9.2.4. Duration and Elapsed Time

Durations (e.g., the duration of an adverse event, duration of exposure, etc.) are calculated as the stop date minus the start date plus one.

For elapsed time (e.g., the time since initial diagnosis):

- If the reference date is on or after the event date, then the elapsed time is the reference date minus the event date + 1.
- If the reference date is before the event date then the elapsed time is the reference date minus the event date.

When reporting time to event (TTE) durations such as duration of response (DOR) in months, divide the number of days by 30.4375; to report in weeks divide the number of days by 7; to report in years divide the number of days by 365.25. These algorithms for time to event return decimal numbers, and ignore the actual numbers of days in the months or years between start date and stop date. The "year" used in these algorithms is 365.25 days long, and the "month" is one twelfth of that year.

For converting all other durations (e.g. duration of adverse events, duration of exposure, age) to weeks, months or years use the following:

- To report the duration in weeks divide the number of days by 7.

- To report the duration in months use:

$$(\text{YEAR}(\text{stopdate}+1) - \text{YEAR}(\text{startdate})) * 12 + (\text{MONTH}(\text{stopdate}+1) - \text{month}(\text{startdate}) - 1) + (\text{DAY}(\text{stopdate}+1) \geq \text{DAY}(\text{startdate}))$$

- To report the duration in years use:

$$\text{intck}(\text{'year'}, \text{startdate}, \text{stopdate}+1) - (\text{month}(\text{stopdate}+1) < \text{month}(\text{startdate}) \text{ or } (\text{month}(\text{stopdate}+1) = \text{month}(\text{startdate}) \text{ and } \text{day}(\text{stopdate}+1) < \text{day}(\text{startdate})))$$

The algorithms above for age and duration return whole numbers for months and years, accurately accounting for the actual numbers of days in the months or years between the start date and the stop date.

9.2.5. Imputation of Partial Dates

Imputed partial dates will not be used to derive study day, duration (e.g. duration of adverse events), or elapsed time variables. In addition, imputed dates are not used for deriving the last contact date in overall survival analysis dataset (ONCSURV).

With the exception of new anti-cancer start date (NEWCTXDT) on the Oncology time to event analysis dataset (ONCTTE) [,][and] exposure end date (EXENDT) on the Exposure analysis dataset, [and other variables and datasets] imputed dates will also not be stored on datasets.

Imputed dates will not be displayed in listings. However, where necessary, display macros may impute dates as temporary variables for the purpose of sorting data in listings only. In addition partial dates may be imputed for 'slotting' data to study time periods (Section 9.3) or for specific analysis purposes as outlined below.

The partial date imputation will follow Analysis Data Model (ADaM) conventions. The ADaM approach is to populate the numeric date variables with the imputed date and add a flag variable to the dataset that indicates the level of imputation. The flag variable can contain the values: blank, 'D', 'M', 'Y'.

Blank: indicates that no imputation was done

D='Day': indicates that the day portion of the date is imputed

M='Month': indicates that the month and day portions of the date are imputed
 Y='Year': indicates that the entire date (year, month, and day) is imputed

Example of Date Variables: Date of new anti-cancer therapy
 NEWCTXD_ - character date variable
 NEWCTXDT - numeric date variable
 NEWCDTFL - flag variable

Details on imputing partial dates for specific datasets are outlined below.

Adverse Events (AE):

Imputations in AE are used for slotting events to the appropriate study time periods and for sorting in data listings.

Dataset	Date	Missing Element	Rule
Adverse Events (AE)	Start Date	day, month, and year	
 • No Imputation for completely missing dates
		day, month	
 • If study treatment start date is missing (i.e. subject did not start study treatment), then set start date = January 1. • Else if study treatment start date is not missing: 
 ○ If year of start date = year of study treatment start date then 
 • If stop date contains a full date and stop date is earlier than study treatment start date then set start date = January 1. • Else set start date = study treatment start date. ○ Else set start date = January 1.
		day	
 • If study treatment start date is missing (i.e. subject did not start study treatment), then set start date = 1st of month. • Else if study treatment start date is not missing: 
 ○ If month and year of start date = month and year of study treatment start date then 
 • If stop date contains a full date and stop date is earlier than study treatment start date then set start date= 1st of month. • Else set start date = study treatment start date. ○ Else set start date = 1st of month.
	End Date		
 • No imputation for partial end dates will be performed

Anti-Cancer Therapy (CTX) and Radiotherapy (RADIO):

Start and end dates are generally not imputed. If start or end dates need to be imputed for an analysis (e.g. to calculate duration or elapsed time as covariates for efficacy analyses), the rules for imputation will be defined within the algorithm of the derived covariate. Additionally, post treatment CTX and RADIO start dates may be imputed to determine date of new anti-cancer therapy. In this case only, NEWCTXDT (not all CTX and RADIO start dates) will be stored on appropriate efficacy datasets. Imputed partial dates will not be used to derive ATMPCTX (time since most recent prior therapy). In addition, the CTXTRTCD variable, and not any variables which use imputed partial dates, will be used to differentiate prior and follow-up CTX and RADIO.

Dataset	Date	Missing Element	Rule
Anti-Cancer Therapy (CTX) Radiotherapy (RADIO)	Start Date	day, month, and year	No Imputation for completely missing dates
		day, month	If partial date contains a year only set to January 1st.
		day	If partial date contains a month and year set to the 1 st of the month.
	End Date		No imputation for partial end dates will be performed

Surgery:

SURGERY date is generally not imputed. If SURGERY date needs to be imputed for an analysis (e.g. to calculate duration, elapsed time as covariates for efficacy analyses, or if surgery is on a lesion being tracked), the rules for imputation will be defined within the algorithm of the derived covariate. Additionally, post treatment SURGERY dates may be imputed (where applicable) to determine date of new anti-cancer therapy. In this case only, NEWCTXDT (not specific SURGERY date) will be stored on appropriate efficacy datasets. The SPCATCD variable, and not any variables which use imputed partial dates, will be used to differentiate prior, on, and follow-up SURGERY data. The derived ATTYPE and ATTYPECD variables are not needed for reporting of data because SPCATCD can be used. Therefore, imputed dates are not needed for derivation of ATTYPE and ATTYPECD.

Dataset	Missing Element	Rule
Surgery	day, month, and year	
 No Imputation for completely missing dates
	day, month	
 If partial date contains a year only set to January 1st.
	day	
 If partial date contains a month and year set to the 1st of the month

Concomitant Medication (Conmed) and Blood and Blood Supportive Care Products:

Impute start and end dates for use in derivation of the reference variables (CONMEDS.CMSTRF/BLDPROD.BLSTRF, CONMEDS.CMENRF/BLDPROD.BLENRF), but do not permanently store the imputed start and end dates in the CONMEDS and BLDPROD AR datasets. The reference variables will be used to differentiate before, during and after for the concomitant medication start and end dates. The derived ATTYPE and ATTYPECD variables are not needed for reporting of data.

Dataset	Date	Missing Element	Rule
Concomitant Medication (Conmed) Blood and Blood Supportive Care Products (BLDPROD)	Start Date	day, month, and year	
 No Imputation for completely missing dates
		day, month	
 If study treatment start date is missing (i.e. subject did not start study treatment), then set start date = January 1. Else if study treatment start date is not missing: 
 If year of start date = year of study treatment start date then 
 If stop date contains a full date and stop date is earlier than study treatment start date then set start date = January 1. Else set start date = study treatment

			
start date.
 
 ○ Else set start date = January 1.
		day	
 • If study treatment start date is missing (i.e. subject did not start study treatment), then set start date = 1st of month. • Else if study treatment start date is not missing: 
 ○ If month and year of start date = month and year of study treatment start date then 
 ▪ If stop date contains a full date and stop date is earlier than study treatment start date then set start date= 1st of month. ▪ Else set start date = study treatment start date. ○ Else set start date = 1st of month.
	End Date	day, month, and year	
 • No Imputation for completely missing dates
		day, month	
 • If partial end date contains year only, set end date = earliest of December 31 or date of last contact.
		day	
 • If partial end date contains month and year, set end date = earliest of last day of the month or date of last contact (MSTONE.LCONTDT).

ONCTTE, RESP2, and RESP2EX1:

Start dates for follow-up CTX, RADIO (where applicable), and SURGERY (where applicable) will be temporarily imputed in order to define event and censoring rules for progression-free survival, response rate, or duration of response (i.e. start date for new anti-cancer therapy). Dates will only be imputed when a month and year are available but the day is missing. The imputed date(s) will not be stored on the CTX, RADIO, or SURGERY datasets. The following rules will be used to impute the date when partial start dates are present on CTX RADIO, and/or SURGERY:

Dataset	Date	Missing Element	Rule
Anti-Cancer Therapy (CTX) Where applicable: Radiotherapy	Start Date	day, month, and year	
 • No Imputation for completely missing dates

(RADIO) Surgery			
		day, month	
 No imputation for missing day and month (note the eCRF should only allow for missing day)
		day	
 If partial date falls in the same month as the last dose of study treatment, then assign to earlier of (date of last dose of study treatment+1, last day of month). If partial date falls in the same month as the subject's last assessment and the subject's last assessment is PD, then assign to earlier of (date of PD+1, last day of month). If both rules above apply, then assign to latest of the 2 dates Otherwise, impute missing day to the first of the month.
	End Date		
 No imputation for partial end dates will be performed

NEWCTXDT is derived as the earliest date of new anti-cancer therapy (e.g. chemotherapy), radiotherapy (where applicable), or cancer related surgical procedure (where applicable) and will include imputed dates. If NEWCTXDT is an imputed date, then the flag variable NEWCDTFL is assigned the value of 'D' to indicate that the day portion of the date is imputed (following ADaM convention).

As multiple dates are used to derive NEWCTXDT ensure that NEWCDTFL is only set to 'D' if the derived date is imputed. For example if the date of new radiotherapy is imputed but the date of new anti-cancer therapy is prior to date of new radiotherapy and the new anti-cancer therapy date is not a partial date then the NEWCDTFL should be set to missing as the date used for NEWCTXDT is not an imputed date.

Covariates:

If the algorithms for covariates (e.g. prognostic factors) include any partial dates, then the algorithms must specify the date imputation rules used in the derivations. The following imputation rules are the standard rules to be used when algorithms for covariates require date imputations.

Variable	Example of when to impute	Rule
Prior CTX start date Prior RADIO start date	
 • Impute to derive duration 
 ○ Duration of prior [Herceptin] Therapy 	
 • Only impute when a month and year are available but the day is missing. • Impute to first day of the month. • Do not store imputed date • Use only for relevant efficacy analyses (i.e. not to be used for general radiotherapy or anti-cancer therapy summaries)
Prior CTX end date Prior RADIO end date	
 • Impute to derive elapsed time and duration 
 ○ Duration of prior [Herceptin] Therapy ○ Time from Last dose of [Herceptin] to Randomization 	
 • Only impute when a month and year are available but the day is missing. • Impute to last day of the month, also must be prior to 'start' 
 ○ if 'start' is the first of the month assign to 'start', else assign to 'start'-1), where 'start' is either the date of randomization or the start of study treatment. • Do not store imputed date • Use only for relevant efficacy analyses (i.e. not to be used for general radiotherapy or anti-cancer therapy summaries)
Any DISCHA1 dates. For example: 
 • DIAGDT • LSTRECDT • LPROGDT 	
 • Impute to derive elapsed time 
 ○ Time from initial diagnosis to randomization for use as a covariate ○ Time from progression on last therapy until randomization for use as a covariate 	
 • If both month and day are missing, impute to January 1st else if day is missing, impute to first day of the month. • Do not store imputed date • Use only for relevant efficacy analyses (i.e. not to be used for general disease characteristic summaries)

9.2.6. Imputation of Missing Exposure End Dates

In general, completely missing dates are not imputed. However, subjects in oncology trials may still be on study treatment when analyses are performed and so may have missing exposure end dates in their last dosing record. Missing exposure end dates for subjects who are still on study treatment at the time of an analysis will be imputed. For subjects with missing exposure end dates at the time of data cutoff, the exposure end date will be imputed to the earliest of: the date of the data cutoff, the date of withdrawal from the study, or the death date. The imputed exposure end date will be used to calculate cumulative dose and exposure duration. The imputed exposure end date will be stored in the EXPOSURE analysis dataset (EXENDT) and an exposure end date imputation flag variable will be derived indicating which exposure end date records are imputed. Imputed exposure end dates will also be stored on the MSTONE analysis dataset (MSTENDT).

For subjects who have missing end dates in their last exposure record because they are still on study treatment, the on-therapy indicator variables ATTYPE and ATTYPECD are assigned to on-therapy for all records where the 'dataset'.date' is after or on the study treatment start date.

9.2.7. Baseline Definition

Baseline will be defined as the most recent non-missing value prior to the first dose of study treatment. For laboratory data, baseline will be defined as the most recent non-missing value from a central laboratory prior to the first dose of study treatment.

The following table indicates the baseline day to be used in any change from baseline listings / summaries / graphical presentations or as a covariate in a statistical analysis:

Parameter	Baseline Days Collected		Baseline To Be Used in Analysis / Summaries
	Screening ¹	Day 1	
Safety :			
ECOG	X		Screening
Brain Magnetic Resonance Imaging (MRI) /Computed Tomography (CT)	X (5 weeks)		Screening
Lesion Assessment	X (5 weeks)		Screening
Vital Signs	X		Screening ²
Physical examination	X		Screening ²
Ophthalmic examination	X		Screening ²
ECG	X (5 weeks)		Screening
ECHO	X (5 weeks)		Screening
Chemistry and Haematology ³	X		
PD :			
Tumor		X	Day 1
Skin		X	Day 1
Blood sample for biomarker		X	Day 1
Blood sample for circulating free DNA (cfDNA)		X	Day 1
Clinical Activity:			
Disease Assessment	X		Screening

1. ≤ 28 days before 1st dose except where noted
2. Use the mean of replicate assessments at any given time point as the value for that time point in all summaries, figures and statistical analyses.
3. Screening labs performed within 2 weeks prior to randomization do not need to be repeated

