- 11. Adverse events will be recorded from the time the first dose of study treatment is administered until 30 days after discontinuation of study treatment. Serious adverse events will be collected over the same time period as AEs except SAEs assessed as related to study participation (e.g., protocol-mandated procedures, invasive tests, or change in existing therapy), study treatment, or a GSK concomitant medication which must be recorded from the time a patient consents to participate in the study up to and including any follow-up contact.
- 12. At each timepoint listed, a single 12-lead ECG will be performed by qualified site personnel after the patient has rested in a semi-recumbent or supine position for at least 5 minutes.
- 13. While on treatment, patients who have an asymptomatic, absolute decrease in LVEF of > 10% compared to screening and whose ejection fraction is below the institution's LLN, must be followed according to LVEF guidelines for study drug management and requirements for subsequent ECHO.
- 14. All medications the patient takes during the study from the time of screening until 30 days after the last dose of study treatment will be recorded.
- 15. Analysis of clinical chemistry and haematology samples will be performed by the local lab. Screening labs performed within 2 weeks prior to randomisation do not need to be repeated.
- 16. Serum pregnancy test is required at Screening. Subsequent tests may be urine tests, and should be performed as clinically indicated.
- 17. A 4-week supply of study medication should be dispensed at each scheduled study visit as of Day 1. Patients should be provided with dosing instructions. Patients should start treatment as soon as possible after randomisation but no later than 72 hours post-randomisation.
- 18. Patients should be instructed to return study drug vials at each visit; compliance will be assessed through querying the patient and through pill count at the time of new dispensation. Dose modifications and interruptions must be recorded.
- 19. The date and exact time of PK sample collection and most recent dose will be recorded. Details of collection procedures, including dosing instructions for morning and afternoon visits, will be provided in the SPM.
- 20. End of study assessments do not need to be repeated if performed within 4 weeks
- 21. Biomarker-related sampling to be conducted at randomisation to avoid biomarker sample collection for ineligible patients

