# 7.4.4. Laboratory Assessments

All protocol-required laboratory assessments must be conducted in accordance with the Time and Events Schedule (Table 19). Only local laboratory assessments are undertaken during the course of the trial and its data must be recorded in the patients CRF.

Clinical chemistry and haematology parameters to be tested are listed in Table 22. Female patients of child-bearing potential will have a serum pregnancy test at Screening; urine pregnancy testing may be done during study treatment, if necessary.

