9.2.8. Change from baseline

Change from baseline will be presented for safety data as described in Section 12.

Change from baseline is calculated as:

- For records occurring after baseline: (visit value) – baseline value.

Percent change from baseline is calculated as:

- For records occurring after baseline: ((change from baseline) / baseline value) * 100

If either the baseline or visit value is missing, the change from baseline and/or percent change from baseline is set to missing as well.

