9.2.9. Multiple Assessments

All data will be reported according to the nominal visit date for which it was reported (that is, no visit windows will be applied during dataset creation). Unscheduled data is included only in summary sections and in shift summaries of laboratory (e.g., vital signs/ECG) data labelled worst- case. For summaries that collapse data across multiple planned time intervals, select the worst-case data at each collapsed interval.

If multiple assessments on different days are reported for the same scheduled assessment, then the latest assessment for that scheduled assessment will be analyzed.

If multiple assessments are reported on the same date for the same scheduled planned time, then the worst-case result will be analyzed, with the exception of laboratory data reported from both central and local laboratories. If laboratory data is reported from both central and local laboratories with the same date, then the central laboratory data will be analyzed to provide consistency with measurements from other subjects. For example, for ECG data where 3 assessments are collected for each scheduled planned time, the first 3 measures will be used to compute the mean values for ECG intervals at each scheduled planned time.

Data from all assessments (scheduled and unscheduled), including multiple assessments, will be included in listings.

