Summaries of worst case grade increase from baseline grade will be provided for all the lab tests that are gradable by CTCAE v4.0. These summaries will display the number and percentage of subjects with a maximum post baseline grade increasing from their baseline grade. Any increase in grade from baseline will be summarized along with any increase to a maximum grade of 3 and any increase to a maximum grade of 4. Missing baseline grade will be assumed as grade 0. In addition, the summary will include grade increase from baseline by scheduled visits. For laboratory tests that are graded for both low and high values, summaries will be done separately and labeled by direction, e.g. sodium will be summarized as hyponatremia and hypernatremia.

For lab tests that are not gradable by CTCAE v4.0, summaries of worst case changes from baseline with respect to normal range will be generated. Decreases to low, changes to normal or no changes from baseline, and increases to high will be summarized at each scheduled visit as well as for the worst case post baseline. If a subject has a decrease to low and an increase to high during the same time interval, then the subject is counted in both the “Decrease to Low” categories and the “Increase to High” categories. In addition, the summary will include worst case changes from baseline with respect to normal range by scheduled visits.

Separate summary tables for hematology, chemistry, liver function, and coagulation, laboratory tests will be produced.

Detailed derivation of baseline assessment is specified in Section 9.2.

Unless otherwise specified, the denominator in percentage calculation at each scheduled visit will be based on the number of subjects with non-missing value at each particular visit.

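### SAP 9.2.7 takes the laboratory baseline only from a central laboratory, but the protocol uses local laboratories only; read as written, laboratory change from baseline is missing and some patients who do not worsen count as grade increases

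*SAP*

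**What the plan says.** SAP 9.2.7 opens with a general rule: baseline is the last available value before treatment starts, from any source. The next sentence replaces that rule for laboratory tests: "baseline will be defined as the most recent non-missing value from a central laboratory prior to the first dose of study treatment".

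The protocol describes a different source. Section 7.4.4 states: "Only local laboratory assessments are undertaken during the course of the trial". Footnote 15 of Table 19 agrees: "Analysis of clinical chemistry and haematology samples will be performed by the local lab".

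Three further SAP rules bear on the outcome:

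- SAP 9.2.9 contains the only other sentence that ranks the two kinds of laboratory: "If laboratory data is reported from both central and local laboratories with the same date, then the central laboratory data will be analyzed".
- SAP 9.2.8, on numerical change: "If either the baseline or visit value is missing, the change from baseline and/or percent change from baseline is set to missing as well".
- SAP 12.7, on gradable tests: "Missing baseline grade will be assumed as grade 0". For the definition of baseline, the same section refers back: "Detailed derivation of baseline assessment is specified in Section 9.2".

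For tests without a CTCAE grade, SAP 12.7 plans categorical shifts: "Decreases to low, changes to normal or no changes from baseline, and increases to high will be summarized at each scheduled visit".

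**The concern.** The SAP bases the laboratory baseline on a data source that the protocol excludes. A programmer has two choices. One is to follow the rule, find no baseline, and let the missing-data conventions act on every patient. The other is to use the local value without any text that permits it.

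The grade-0 convention is a sensible default for an occasional gap. Applied to everyone, it would turn abnormalities already present at entry into apparent on-treatment worsening. Characterising safety is a secondary objective, and chemistry and haematology values are named in its endpoint, so these tables should be derivable from the plan as it stands.

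**Working it through.** The plan states no figure that depends on the laboratory baseline, so there is nothing to reproduce. The check is a comparison of rules followed by an enumeration.

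**1. Is there a qualifying baseline?**

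| Question | Source | Answer |
|---|---|---|
| Which value is the laboratory baseline? | SAP 9.2.7 | Central laboratory only |
| Where are the tests run? | Protocol 7.4.4; Table 19, footnote 15 | Local laboratories only |
| Does 9.2.9 supply a fallback? | SAP 9.2.9 | No; it breaks ties when both sources share a date |
| Does 12.7 define its own baseline? | SAP 12.7 | No; it points back to Section 9.2 |

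Read as written, no chemistry, haematology or liver-function test has a baseline. LDH and CRP are uncertain. Protocol 7.2.1 also lists them as blood biomarkers and does not say which laboratory measures those samples.

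**2. Numerical change (Tables 3.3010–3.3012).** Under 9.2.8 the change is missing for every patient with no baseline. The visit values in the same tables are unaffected.

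**3. Grade changes (Tables 3.3020–3.3022).** Let b be the entry grade and m the worst later grade, each from 0 to 4, which gives 5 × 5 = 25 pairs.

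- A true increase is m > b.
- As written, b is missing and set to 0, so an increase is m > 0.
- The two disagree exactly when 1 ≤ m ≤ b. For b = 1, 2, 3, 4 that is 1 + 2 + 3 + 4 = 10 pairs: (1,1), (2,1), (2,2), (3,1), (3,2), (3,3), (4,1), (4,2), (4,3), (4,4).
- The other 15 are classified correctly: 5 with b = 0, 4 with b ≥ 1 and m = 0, and 6 with m > b ≥ 1.

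A patient who improves from grade 2 to grade 1 is therefore reported as having increased. With the local pre-dose value as baseline, 0 of 25 pairs are wrong. The 10 of 25 is a count of possibilities, not a patient rate.

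**4. Normal-range shifts (Tables 3.3030–3.3031).** Separating no change from an increase to high needs a baseline. The grade-0 convention does not apply to ungraded tests, and no other rule covers a missing baseline here. The shifts cannot be derived.

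**5. How many patients?** Abnormal entry values are allowed: Table 2 of the protocol admits AST and ALT up to 2.5 × ULN. The documents do not give the share entering at grade 1 or more, or how many of those stay at grade 1 or more without worsening. As an illustration only, take 54 / 3 = 18 patients per arm and assume that 20% truly worsen on a test (18 × 0.20 = 3.6). Let s be the assumed share who enter at grade 1 or more, remain at grade 1 or more and do not worsen:

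| s | Reported as increased | Of 18 |
|---|---|---|
| 5% | 20% + 5% = 25% | 4.5 |
| 10% | 20% + 10% = 30% | 5.4 |
| 20% | 20% + 20% = 40% | 7.2 |
| 40% | 20% + 40% = 60% | 10.8 |

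**The case against.** The best defence is that the sentence is leftover template text. The same SAP keeps a bracketed name of a drug not used in this trial (9.2.5), questionnaires that the protocol does not schedule (9.3.1) and references to expansion cohorts (13.3.1). Other text points to local screening values: the 9.2.7 table lists chemistry and haematology at screening, and 12.7 treats coagulation as collected at baseline. A baseline that is empty for every patient would be hard to miss in programming, and SAP 8.1 requires departures from the plan to be identified in the study report. The separate dataset specifications mentioned in SAP 9.2 might also settle the matter; they are not available to check.

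Much of this stands. Local values were probably intended, and the practical risk is modest. It does not make the stated rule workable, because the override is explicit and nothing in either document withdraws it.

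Three stronger readings are tempting but unsupported:

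- **That every patient who enters at grade 1 or more without worsening is miscounted.** A patient who is grade 0 at every later assessment is classified correctly.
- **That SAP 9.2.8 sets the normal-range shifts to missing.** It defines numerical and percentage change. The shifts are categorical, and the SAP is silent on them.
- **That a count of misplaced LDH results can be given.** The protocol's background sections report LDH above ULN in 33% of patients in the dabrafenib phase III trial and in 52% of treatment-naive melanoma patients in Part B of the combination study. These rates would give 18 × 0.33 = 5.9 and 18 × 0.52 = 9.4 patients per arm entering high. Calling them wrongly shown as increased requires a missing baseline to be read as normal, which no passage says. LDH is also one of the two tests whose laboratory is uncertain.

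The baseline cell for chemistry and haematology in the 9.2.7 table appears blank. That may be a fault of text extraction, and nothing here rests on it.

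**Conclusion.** The contradiction is real and lies in the current text of both documents. Followed literally, the SAP gives no chemistry, haematology or liver-function baseline, subject to the uncertainty over LDH and CRP. The numerical change summaries are then empty, the grade-change tables count some stable or improving patients as increases, and the normal-range shifts cannot be derived. No patient count can be drawn from the documents.

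The reach is narrow. The primary p-ERK endpoint has its own Day 1 baseline. Efficacy, adverse events, maximum-grade laboratory tables and visit values do not use this baseline, and the study is descriptive with no treatment comparison. Severity is minor. The conclusion assumes that the SAP is applied as written and that the dataset specifications do not already override it.

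**What to change.** 1. In SAP 9.2.7, delete the central-laboratory sentence so that the general rule applies, or change its source to the local laboratory.
2. Enter Screening in the chemistry and haematology baseline cell if it is blank in the original.
3. Align the central-over-local sentence in SAP 9.2.9, so that safety chemistry, including LDH and CRP, uses local values throughout. This matters most where biomarker and safety sampling coincide, for example at Week 8. SAP 12.7 lists CRP as chemistry but Table 22 of the protocol does not, so confirm that a local CRP value will exist.

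The cost is two sentences and at most one table cell in the SAP. No data collection or patient procedure changes.
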